9.1.1.9. Tender/Swollen Joint Count (28 Joints)

The 28 joints to be examined and assessed as tender or not tender for tender joint count and as swollen or not swollen for swollen joint count include 14 joints on each side of the patient's body: the 2 shoulders, the 2 elbows, the 2 wrists, the 10 metacarpophalangeal joints, the 2 interphalangeal joints of the thumb, the 8 proximal interphalangeal joints, and the 2 knees.

9.1.1.10. Systemic Lupus International Collaborating Clinics/American College of Rheumatology Damage Index

The SLICC/ACR Damage Index is scored on 41 items representing damage to 12 organ systems. The index records damage occurring in patients with SLE regardless of its cause and includes specific comorbidities associated with SLE that may be due to treatment-related toxicity.

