		Total Damage Score	Calculated within tablet system with edit checks; no additional derivation.	Within tablet system: if any item scores, but not all, are missing then impute a score of 0 for the missing item(s). For completely missing questionnaires, data can be carried forward if obtained within 36 days of visit; otherwise missing.
Lupus Low Disease Activity State (LLDAS)	The LLDAS is a composite measure designed to identify patients achieving a state of low disease activity.	LLDAS	
 
SLEDAI-2K <math>\leq 4</math> with no activity in SLEDAI-2K major organ systems (CNS, Vascular, Renal, cardiorespiratory, and constitutional), where “no activity” is defined as all items of SLEDAI-2K within these major organ systems = 0.
 
No new features of Lupus disease activity in SLEDAI-2K compared to previous occurred visit, where the “new feature” is defined as any of SLEDAI-2K 24 items changed from 0 to <math>>0</math>.
 
PGA <math>\leq 1</math>
 
Current prednisone or equivalent dose <math>\leq 7.5</math> mg/day
 
	Missing if any component remains missing after each instrument-level imputation rule is applied.
SFI flare	The SFI uses the SLEDAI score, disease activity scenarios, treatment changes, and PGA to define mild/moderate and severe flares.	SFI flare	Not derived; used as entered.	The absence of a flare record, or ‘Not Applicable’, both are indicative of no occurrence of flare.
		Annualized flare rate	Calculated as the number of SFI flares divided by the flare exposure time in days multiplied by 365.25.	No minimum data requirement.
Tender/Swollen Joint Count (28 Joints)	28 joints are assessed as tender only, swollen only, tender and swollen, not evaluable.	Tender Joint Count 28/ Swollen Joint Count 28	The number of tender and swollen joints will be calculated by summing all joints respectively.	For patients who have an incomplete set of joints evaluated, the joint count will be adjusted to a 28-joint count for tenderness and a 28-joint count

Measure	Description	Variable	Derivation/Comment	Definition of Missing
				for swelling by dividing the number of affected joints by the number of evaluated joints and multiplying by 28.

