Systemic Lupus International Collaborating Clinics/American College of Rheumatology Damage Index (SLICC/ACR)	SLICC/ACR Damage Index assesses damage to 12 organ systems regardless of its cause.	SLICC/ACR Damage Index Score	Calculated as the sum of all available entries with a maximum score of 47.	“Missing” item is coded as 0.
Worst Pain NRS	This Worst Pain NRS is a single-item patient-administered 11-point horizontal scale anchored at 0 (no pain) and 10 (pain as bad as you can imagine)	Worst Pain NRS score	Permitted range of values is from 0 to 10.	Single item, missing if missing.
FACIT-Fatigue	The FACIT-Fatigue scale (Cella and Webster 1997) is a 13-item symptom-specific questionnaire that assesses self-reported severity of fatigue and its impact upon daily activities and functioning.	FACIT-Fatigue total score	The FACIT-F uses 0 (“not at all”) to 4 (“very much”) numeric rating scales to assess fatigue and its impact in the past 7 days. Scores range from 0 to 52 with higher scores indicating less fatigue. The FACIT-Fatigue Scoring Guidelines (Version 4) will be used to calculate the Total Score. Reversals are needed for all items except An5 and An7, as described in scoring manual. http://www.ser.es/wp-content/uploads/2015/03/FACIT-F_INDICE.pdf .	Missing items are acceptable as long as more than 50% of the items are answered (ie, a minimum of 7 out of 13 items), the sum of available items will be multiplied by 13 then divided by the number of items answered to obtain the total score. If less than 7 items are answered, the FACIT-Fatigue total score will be set to missing.
Steroid sparing	This measures the change in corticosteroid dose through week 156	Corticosteroid Dose	See Section 6.10.1 for detailed derivations.	No minimum data requirement.
Worst Joint Pain NRS	This Worst Joint Pain NRS is a single-item, patient-administered 11-point horizontal scale anchored at 0	Worst Joint Pain NRS Score	Permitted range of values is from 0 to 10.	Single item, missing if missing.

Measure	Description	Variable	Derivation/Comment	Definition of Missing
	(no joint pain) and 10 (joint pain as bad as you can imagine)			
Worst Fatigue NRS	This Worst Fatigue NRS is a patient-administered 11-point horizontal scale anchored at 0 (no fatigue) and 10 (fatigue as bad as you can imagine)	Worst Fatigue NRS Score	Permitted range of values is from 0 to 10.	Single item, missing if missing.

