**Table JAIM.6.4. Description of Efficacy/Health Outcomes Analyses**

Measure	Variable	Analysis Method	Population	Key Time Point(s) a
SRI-4	Proportion of patients achieving SRI-4 response	Descriptive analysis with observed and NRI	mITT, patients with SLEDAI-2K score of $\geq 4$ at baseline	Week 156 visit
SRI-x (where x is 5, 6, 7, 8)	Proportion of patients achieving SRI-x response	Descriptive analysis with observed and NRI	mITT, patients with SLEDAI-2K score of $\geq x$ at baseline	Week 156 visit
SLEDAI-2K	Change from baseline in mean total SLEDAI-2K through Week 156	MMRM	mITT	Week 156 visit
	Proportion of patients achieving reduction of $\geq 4$ points from baseline	Descriptive analysis with observed and NRI	mITT, patients with SLEDAI-2K score $\geq 4$ at baseline	Week 156 visit
	Proportion of patients with improvement in each SLEDAI-2K individual organ systems vs baseline	Descriptive analysis with observed and NRI	mITT, patients with SLEDAI-2K score $> 0$ within the organ domain at baseline	Week 156 visit
	Proportion of patients with worsening in each SLEDAI-2K individual organ system vs baseline	Descriptive analysis with observed and NRI	mITT, patients with at least 1 SLEDAI-2K item = 0 in the organ domain at baseline	Week 156 visit
BILAG	Proportion of patients with no new BILAG A and no more than 1 new BILAG B disease activity score (compared with baseline)	Descriptive analysis with observed and NRI	mITT	Week 156 visit
	Proportion of patients with improvement in each BILAG individual organ system vs baseline	Descriptive analysis with observed and NRI	mITT, patients with BILAG A or B in the organ domain at baseline	Week 156 visit
	Proportion of patients with worsening in each BILAG individual organ system vs baseline	Descriptive analysis with observed and NRI	mITT, patients without BILAG A in the organ domain at baseline	Week 156 visit
PGA	Proportion of patients with no worsening in PGA (compared with baseline)	Descriptive analysis with observed and NRI	mITT	Week 156 visit
	Change from baseline in PGA score over time through Week 156	MMRM	mITT	Week 156 visit
BICLA	Proportion of patients achieving BICLA response	Descriptive analysis with observed and NRI	mITT	Week 156 visit
28 Tender/Swollen Joint Count	Change from baseline in tender joint count	MMRM	mITT	Week 156 visit
	Change from baseline in swollen joint count	MMRM	mITT	Week 156 visit

Measure	Variable	Analysis Method	Population	Key Time Point(s) a

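### Joint counts are scaled up to 28 with no minimum number of joints evaluated, so a sparse examination gives an unreliable count in either direction; the effect is probably small, and a one-line limit would remove it.

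*SAP*

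**What the plan says.** Protocol Section 9.1.1.9 lists the joint set (14 on each side) and how each is rated: "The 28 joints to be examined and assessed as tender or not tender for tender joint count", and likewise for swelling. It has no rule for an incomplete examination.

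SAP Table JAIM.6.3 foresees incomplete examinations. It describes the assessment as "28 joints are assessed as tender only, swollen only, tender and swollen, not evaluable". The rule follows in the column that defines missingness: "For patients who have an incomplete set of joints evaluated, the joint count will be adjusted to a 28-joint count for tenderness", and similarly for swelling, "by dividing the number of affected joints by the number of evaluated joints and multiplying by 28". No lower limit is attached, and the cell does not say when the count itself is missing. SAP Sections 6.3, 6.4 and 6.4.2 add no limit for joint counts.

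Two other kinds of entry in the same column are useful for comparison. FACIT-Fatigue is also prorated, but with a floor: "Missing items are acceptable as long as more than 50% of the items are answered", and "If less than 7 items are answered, the FACIT-Fatigue total score will be set to missing". For the annualized flare rate and the corticosteroid dose the cell reads "No minimum data requirement". The joint-count row says neither.

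The prorated counts feed two secondary endpoints in SAP Table JAIM.6.4: "Change from baseline in tender joint count", and the same for swollen joints. Both use the MMRM in the mITT population, with Week 156 as the key time point. They are the only endpoints under the musculoskeletal objective.

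**The concern.** Proration treats the joints that were not evaluated as if they resembled those that were. With 26 or 27 of 28 joints examined, the assumption hardly matters. With a handful examined, the result depends almost wholly on it, yet the record enters the MMRM like any complete count. The rule as written allows a score at the top of the scale, or at zero, from one joint.

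At a postbaseline visit, such a record distorts that visit's mean and inflates its variance. At baseline, it carries into that patient's change score at every later visit. What the plan reports for these endpoints is each arm's LS mean change, with a test against zero. SAP Section 6.1 plans no between-arm comparison, so a stray record affects an arm's own estimate directly.

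**Working it through.** The plan gives no figure to reproduce. The check evaluates its formula.

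**Inputs**
- Rule: scaled count = affected / k × 28, where k is the number of joints evaluated (SAP Table JAIM.6.3).
- Enrolment of about 1100 (Protocol Section 10.1; SAP Section 5.2).
- Four arms (SAP Table JAIM.6.1), with originating-study placebo patients re-randomised 1:1.
- Assumption: 1:1:1 allocation in the originating studies, which these documents do not state. Each continuing arm then has 1100/3 ≈ 367 patients at entry, and each placebo-switch arm 367/2 ≈ 183.

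**1. Weight of one affected joint, 28/k**
- k = 27: 1.04
- k = 26: 1.08
- k = 14: 2.00
- k = 7: 4.00
- k = 2: 14.00
- k = 1: 28.00

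The error has no fixed direction. One affected of one evaluated gives 28; if the other 27 are unaffected, the error is +27. None affected of one gives 0; if the other 27 are affected, the error is −27. With k = 0 the formula is 0/0.

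**2. Noise, even if the evaluated joints are a random subset**

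Suppose 8 of 28 joints are truly affected (an illustrative value), so p = 8/28. The scaled count is then right on average, with SD = 28 × √[ p(1 − p)/k × (28 − k)/27 ]:
- k = 27: 0.47
- k = 14: 2.43
- k = 7: 4.22
- k = 1: 12.65 (the score is 28 with probability 8/28 = 28.6%, otherwise 0)

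Proration is therefore harmless near 28 and close to uninformative near 1. Any bias would come on top, and only if the evaluated joints differ from the rest.

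**3. Effect of one extreme record on an arm's raw mean at that visit**

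An error of 27 joints shifts the mean by 27/n:
- n = 183: 0.148, about 0.15
- n = 367: 0.074, about 0.07

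These are sizes at entry. The shift grows as patients leave; at an illustrative n = 100 it is 0.27.

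**4. Effect of the same error at baseline**

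The MMRM in SAP Section 6.4 adjusts for baseline value and its interaction with visit. Let b be the slope of the postbaseline value on baseline. Hold it fixed, and take LS means at the overall mean baseline (both simplifications). A false +27 in one patient shifts the arm's LS mean change by −27/n + (1 − b)(27/n − 27/1100).
- n = 183: −0.148 + (1 − b) × 0.123, which is −0.148 at b = 1, −0.086 at b = 0.5 and −0.025 at b = 0.
- n = 367: −0.074 + (1 − b) × 0.049, which is −0.049 at b = 0.5 and −0.025 at b = 0.

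The patient's own change score is badly wrong, but adjustment removes part of the effect on the reported estimate unless b is 1.

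**5. What a floor does**

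A minimum of 14 evaluated joints caps the multiplier at 28/14 = 2.00. More than 50% of 28 means at least 15, with a cap of 28/15 = 1.87. The FACIT-Fatigue floor of 7 of 13 has almost the same cap, 13/7 = 1.86.

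**The case against.** The best case for leaving the row alone is that sparse examinations are hypothetical. The protocol requires all 28 joints to be rated, and the Schedule of Activities requires a physician to complete the SLE assessments on an electronic device. The ordinary partial record would then lack one or two joints, where the rule works well. With no joints evaluated there is no measurement, and a programmer would set the count to missing. All of this stands, and it is why the point is minor. It does not supply the limit that the rule lacks.

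A reader might go further in four ways that the documents do not support:
- **That one-of-one records are to be expected, or that assessors record mainly the symptomatic joints.** Selective recording would depart from Protocol Section 9.1.1.9, and nothing suggests that it is planned or known to occur.
- **That blank unaffected joints might be read as unevaluated**, because the SAP's category list has no entry for a joint that is neither tender nor swollen. The protocol rates each joint as affected or not, so the list is more likely an incomplete description.
- **That the SAP contradicts itself by giving FACIT-Fatigue a floor.** That floor sits in a row that cites the instrument's own scoring guidelines. CLASI and SLICC/ACR score missing items as 0, and BILAG-2004 assumes absence within most domains once one item is present, all without a 50% floor. The SAP has no general principle that the joint row breaks. FACIT-Fatigue is a useful model, no more.
- **That a false baseline produces a large false improvement in the reported results.** Step 4 shows that this overlooks the covariate adjustment, and baseline errors can also run downward.

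**Conclusion.** The gap is real but minor. The rule has no floor, the row does not say when a count is missing, and neither document fills the gap elsewhere. Proration itself is not at fault and should stay.

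The practical effect is probably small and cannot be determined from the documents, because the frequency of incomplete examinations is not given. The per-record figures of 0.15 and 0.07 joints assume 1:1:1 originating allocation, arm sizes at entry and the largest possible error of 27 joints. They can run in either direction, and several such records would add up or partly cancel. The point touches two secondary endpoints and not the primary safety objective. It is worth correcting because the correction is cheap.

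**What to change.** Add one line to the joint-count row of SAP Table JAIM.6.3: prorate only when about half or more of the 28 joints are evaluated, applied separately to tenderness and swelling. Otherwise set the count to missing at that visit, including when no joint is evaluated. At least 14 joints (cap 2.00), or at least 15 to match the threshold used for FACIT-Fatigue (cap 1.87), would both serve; the sponsor should choose one and state it. Report the number of prorated and missing joint counts by arm, which would also show whether the issue ever mattered.

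The cost is a few more missing counts. At postbaseline visits the planned MMRM handles them under missing at random (SAP Section 6.4.2.3). At baseline, the definition in SAP Section 6.3 falls back on the last nonmissing assessment; if there is none, Section 6.1 already says that no change is calculated. A patient with more than half of the joints persistently not evaluable would drop out of these two analyses, and the by-arm report would make that visible.

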3.2. Background

Systemic lupus erythematosus is a chronic, often debilitating, multisystem, autoimmune disease that is characterized by the presence of autoreactive B cells and elevated autoantibodies, which directly damage the body's cells and tissues. Systemic lupus erythematosus can affect multiple organ systems simultaneously or sequentially, and follows a highly variable clinical course where periods of relatively stable disease are followed by flares and/or periods of persistently active disease; all of which can ultimately lead to irreversible damage to tissues and organ systems.

Systemic lupus erythematosus is predominately a disease affecting women (approximately 9:1 female to male ratio), which can begin at any age but most commonly begins in adolescence or early adulthood (Yu et al. 2017). It affects 20 to 150 people per 1,000,000 people in the US (UpToDate® 2018 [WWW]) and is more common in African-Americans (Lim et al. 2014; Somers et al. 2014), with as many as 1 in 537 African-American women afflicted with SLE (Somers et al. 2014). Additionally, SLE appears to be more severe in African-Americans, Asian-Americans, and Latinos compared to Caucasians (Kaslow 1982; Alarcón et al. 2001).

Clinically, SLE presents with varying signs and symptoms, including fever, arthralgia/arthritis, skin rash, alopecia, pleuritis, pericarditis, nephritis, vasculitis, stroke, seizure, leukopenia, thrombocytopenia, anemia, photosensitivity, and the presence of autoantibodies reactive with nuclear antigens. Fatigue is the most prevalent symptom reported among patients with SLE (Ad Hoc Committee on Systemic Lupus Erythematosus Response Criteria for Fatigue 2007). Pain that interferes with daily living activities is also commonly reported (Özel and Argon 2015). Skin and joint disease are also among the most prevalent features of the illness. Age, African-American race/ethnicity, SLEDAI-2K score, steroid use, and hypertension were associated with transition from no damage to damage, and increase(s) in preexisting damage (Bruce et al. 2015). Over 60% of patients with SLE will develop clinically detectable organ damage within 2 to 7 years of diagnosis, as measured by the Systemic Lupus Erythematosus International Collaborating Clinics (SLICC)/American College of Rheumatology (ACR) damage index (Cooper et al. 2007).

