
 • To evaluate the long-term effect of baricitinib 4-mg or 2-mg QD on mucocutaneous manifestations of SLE. • To evaluate the long-term effect of baricitinib 4-mg or 2-mg QD on musculoskeletal manifestations of SLE. • To evaluate the long-term effect of baricitinib 4-mg or 2-mg QD on individual organ system disease activity. • To evaluate the long-term effect of baricitinib 4-mg or 2-mg QD on damage. • To evaluate the long-term effect of baricitinib 4-mg or 2-mg QD on patient-reported outcomes (PROs). 	
 • Proportion of patients with CLASI total activity score ≥ 10 at baseline with $\geq 50\%$ reduction in CLASI total activity score through Week 156. • Change from baseline in tender joint count through Week 156. • Change from baseline in swollen joint count through Week 156. • Proportion of patients with improvement in each SLEDAI-2K organ system versus baseline through Week 156. • Proportion of patients with worsening in each SLEDAI-2K organ system versus baseline through Week 156. • Change from baseline in SLICC/ACR damage index total score through Week 156. • Change from baseline in Worst Pain NRS through Week 156. • Change from baseline in Worst Joint Pain NRS through Week 156. • Change from baseline in Worst Fatigue NRS through Week 156. • Change from baseline in Patient Global Impression of Severity through Week 156. • Change from baseline in mental component score (MCS), physical component score (PCS), and domain scores in the Short-Form 36-item health survey version 2 (SF- 36v2) acute through Week 156. • Change from baseline in FACIT-F total score through Week 156. • Change from baseline in the EQ-5D-5L through Week 156. • Change from baseline in the WPAI-Lupus through Week 156.

Abbreviations: CLASI = Cutaneous Lupus Erythematosus Disease Area and Severity Index; EQ-5D-5L = 5-level EuroQol-5 Dimensions; FACIT-F = Functional Assessment of Chronic Illness Therapy-Fatigue; LLDAS = Lupus Low Disease Activity State; NRS = Numeric Rating Scale; QD = once daily; SLE = systemic lupus erythematosus; SLEDAI-2K = Systemic Lupus Erythematosus Disease Activity Index 2000; SLICC/ACR = Systemic Lupus Erythematosus International Collaborating Clinics/American College of Rheumatology; SRI-4 = Systemic Lupus Erythematosus Responder Index-4; WPAI = Work Productivity and Activity Impairment.

5. Study Design

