### 6.4.2.4. Modified Last Observation Carried Forward (mLOCF)

For patients who receive prohibited medication, the last nonmissing observation at or before prohibited use will be carried forward to that particular visit interval but not for the subsequent visit intervals (as defined in Section 6.4.2). For all other patients discontinuing from the study or permanently discontinuing the study treatment for any reason, the last nonmissing postbaseline observation on or before discontinuation will be carried forward to that particular visit interval but not for the subsequent visit intervals (as defined in Section 6.4.2). If a patient does not have a nonmissing observed record (or one imputed by other means) for a postbaseline visit, the last postbaseline record prior to the missed visit will be used for this postbaseline visit. If a patient does not have any postbaseline record at a scheduled, unscheduled or early termination visit, they will be excluded from the analysis.

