CLASI Activity Score	The proportion of patients with $\geq 50\%$ reduction from baseline in total activity score	Descriptive analysis with observed and NRI	mITT – patients with CLASI total activity score $\geq 10$ at baseline	Week 156 visit
SFI	Annualized severe flare rate	Descriptive analysis with observed rate	mITT	Week 0 to Week 156 visit
	Annualized severe flare rate	Descriptive analysis with observed rate	mITT	Week 0 to Week 156 visit
	Annualized severe flare rate	Descriptive analysis with observed rate	mITT	Week 0 to Week 156 visit
SLICC/ACR Damage Index Score	Change from baseline in SLICC/ACR Damage Index	Descriptive analysis with observed and mLOCF	mITT	Week 156 visit
LLDAS	Proportion of patients who achieve a LLDAS	Descriptive analysis with observed and NRI	mITT, patients with SLEDAI score of $\geq 4$ at baseline	Week 156 visit
Corticosteroid Sparing	Change from baseline in prednisone dose	MMRM	mITT	Week 156 visit
Worst Pain NRS	Change from baseline in Worst Pain NRS	MMRM	mITT	Week 156 visit
FACIT-Fatigue	Change from baseline in FACIT-Fatigue total score	MMRM	mITT	Week 156 visit
Worst Fatigue NRS	Change from baseline in Worst Fatigue NRS	MMRM	mITT	Week 156 visit
Worst Joint Pain	Change from baseline in Worst Joint Pain NRS	MMRM	mITT	Week 156 visit
Patient Global Impression of Severity	Change from baseline in Patient Global Impression of Severity	MMRM	mITT	Week 156 visit
SF-36 V2 acute	Change from baseline in mental component score (MCS)	MMRM	mITT	Week 156 visit
	Change from baseline in physical component score (PCS)	MMRM	mITT	Week 156 visit
	Change from baseline in domain scores SF-36 health survey version 2 acute	MMRM	mITT	Week 156 visit
EQ-5D-5L	Change from baseline in EQ-5D-5L US/UK population-based index scores and VAS.	MMRM	mITT	Week 156 visit
	Proportion of patients with no problem in each EQ-5D-5L item score	Descriptive analysis with observed and NRI	mITT	Week 156 visit

Measure	Variable	Analysis Method	Population	Key Time Point(s) a
WPAI-Lupus	Change from baseline in WPAI-Lupus	MMRM	For absenteeism score, presenteeism score, and work productivity loss score, population is a subset of mITT that includes patients who had an employment status of Yes at baseline. For activity impairment score, use mITT population	Week 156 visit

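### A missing SLICC/ACR damage item is scored 0 at every visit, so recorded damage can appear to heal, and damage missed at baseline can appear to be new

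*SAP*

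**What the plan says.** The derivation is in the SLICC/ACR row of SAP Table JAIM.6.3 (Section 6.11.1). The total is "Calculated as the sum of all available entries with a maximum score of 47", and a missing "item is coded as 0". The row makes no distinction between baseline and later visits, sets no minimum number of completed items, and has no separate entry for an empty form. The SAP puts the word Missing in quotation marks and does not define it.

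The endpoint in Protocol Table JAIM.2 is "Change from baseline in SLICC/ACR damage index total score through Week 156". It is the only endpoint listed for the damage objective. SAP Table JAIM.6.4 gives its analysis as "Descriptive analysis with observed and mLOCF". Under SAP Section 6.4.2.4, a patient with no non-missing record at a visit is handled as follows: "the last postbaseline record prior to the missed visit will be used for this postbaseline visit".

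On the instrument, Protocol Section 9.1.1.10 states: "The SLICC/ACR Damage Index is scored on 41 items representing damage to 12 organ systems". Protocol Section 3.2 says of flares and persistently active disease: "all of which can ultimately lead to irreversible damage to tissues and organ systems". The same section cites this index as the measure of detectable organ damage. The Schedule of Activities collects it at Week 0, Week 48, Week 156 and early termination.

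**The concern.** If damage is irreversible, a patient's true total cannot fall. Scoring a missing item 0 lets it fall: an item recorded as present at baseline and not assessed at Week 156 contributes a change of minus its score. The opposite error arises when a truly present item is missing at baseline and recorded later, because old damage is then counted as new.

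Both errors enter the one endpoint that answers the damage objective. Other rows of Table JAIM.6.3 are more careful. A SLEDAI-2K item may be carried forward from the preceding 36 days, joint counts are prorated, FACIT-Fatigue needs at least 7 of 13 items, and CLASI, which also scores partial gaps 0, has a separate rule for a wholly missing form.

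**Working it through.** **No figure to reproduce.** The documents give no expected accrual, mean damage score or item-missing rate for this index. What follows from the rule is exact; the cohort sizes are assumptions.

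**One patient, one item worth 1 point, truly present throughout.**
- Recorded at baseline, missing later: 0 − 1 = −1 (apparent healing).
- Missing at baseline, recorded later: 1 − 0 = +1 (false accrual).

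**Does mLOCF help?** It acts when a visit has no non-missing record. Once missing items are set to 0, a partly completed form has a non-missing total, so mLOCF is not triggered. The observed and mLOCF summaries use the same wrong value.

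**Cohort mean.** Let D0 and D1 be the true mean scores at baseline and at the visit, and m0 and m1 the item-missing rates, assumed unrelated to whether an item is present.

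Expected observed change = (1 − m1)·D1 − (1 − m0)·D0

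Bias = m0·D0 − m1·D1

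Assume D0 = 1.0 and true accrual 0.20, so D1 = 1.2:

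| Items missing | Calculation | Observed change | Against 0.20 |
|---|---|---|---|
| 5% after baseline only | 0.95 × 1.2 − 1.0 | 0.14 | −30% |
| 5% at both times | 0.95 × 1.2 − 0.95 × 1.0 | 0.19 | −5% |
| 5% at baseline only | 1.2 − 0.95 × 1.0 | 0.25 | +25% |

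The bias is zero when m0/m1 = D1/D0 = 1.2, and upward above that ratio.

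**Range.** For D0 of 0.5 to 2.0 and accrual of 0.1 to 0.3, 5% missing after baseline only understates accrual by 13% to 105%. At 1% missing, the range is 2.7% to 21%. Equal 5% missingness understates it by 5% throughout. Missingness of 5% at baseline only overstates it by 8% to 100%.

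**Simulation check** (200,000 patients, 41 binary items, D0 = 1.0, accrual 0.20). The three means were 0.14, 0.19 and 0.25. An impossible fall appeared in 4.1% of patients with 5% missing after baseline only, and in 3.6% with 5% missing at both times. Binary items are a simplification: a maximum of 47 on 41 items means that some items can score more than 1.

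**Carry-forward after baseline only.** With 5% missing after baseline only, the loss shrinks to 0.05 × 0.20 = 0.01, giving 0.19 with no falls. It does nothing for items missing at baseline: the third case stays at 0.25. With 5% missing at both times the result is 0.95 × 1.2 + 0.05 × 0.95 × 1.0 − 0.95 × 1.0 = 0.2375, so a baseline rule is needed too.

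**Carry-forward, with items missing at baseline left out of the change.** Expected change = (1 − m0)(1 − m1) × accrual. The three cases give 0.95 × 0.20 = 0.19, 0.95 × 0.95 × 0.20 = 0.18, and 0.95 × 0.20 = 0.19.

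**The case against.** The strongest reply is that the undefined term may make the rule correct. If Missing means a box left unticked because the damage is absent, 0 is the right score. The SAP treats SFI flares in that way: no record means no flare. The documents do not settle which meaning applies, so this stands as a reason to define the term first.

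Three stronger readings are tempting, and the documents do not support them.
- A reader might infer that accrual is understated overall. The rule also applies at baseline, so understatement requires m1·D1 > m0·D0.
- A reader might size the bias as mean score times missing rate. That assumes complete baseline forms and that present items are missed as often as absent ones. With equal missingness at both times the loss is only the missing fraction.
- A reader might infer that an empty form scores 0. The entry is an item rule, and Section 6.4.2.4 deals separately with a visit that has no record. The SAP is silent on an empty form; it does not say that it scores 0.

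Two practical points have some force. Physician scales are captured on an electronic device, and Protocol Appendix 3.2 plans computer edit checks, so gaps may be few; however, no check is specified for this index. A fall in the total would also be visible to anyone who looked, but nothing in the plan requires that.

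The stakes are modest. Efficacy is not a primary outcome, the endpoint is summarised descriptively, and SAP Section 6.1 plans no between-arm inference by default.

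**Conclusion.** The concern holds in a two-sided form. If missing means not assessed, the stated rule gives a wrong value whenever a truly present item is missing, and neither planned analysis corrects it. Recorded damage can appear to heal, and damage missed at baseline can appear to be new.

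The direction and size of the net bias cannot be found from the documents. The results of 0.14, 0.19 and 0.25 against 0.20 rest on an assumed baseline mean of 1.0, assumed accrual of 0.20, 5% missingness, and missingness unrelated to presence. The irreversibility premise comes from the protocol's background section; the description of the index in Section 9.1.1.10 does not use the word.

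The change is worth making because the rule is stated, the error is avoidable with data already collected, and this is the only endpoint for the damage objective. It does not affect the primary safety objective.

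**What to change.** Amend the SLICC/ACR row of SAP Table JAIM.6.3:

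1. Define missing as not assessed, as distinct from unticked because the damage is absent.
2. At post-baseline visits, carry forward the last non-missing score of that item, from JAIM or the originating study. Score 0 only if the item was never recorded as present. A 36-day limit would not work here: the scheduled visits are on Days 1, 337 and 1093, so the gaps are 336 and 756 days.
3. For an item missing at baseline, use an earlier recorded value if there is one. Otherwise leave that item out of the patient's change score, or flag the patient in a sensitivity summary.
4. State that a form with no items completed gives a missing total, then handled by mLOCF.
5. Flag any fall in the total for data query, and report how many items were missing by visit and arm.

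A small understatement remains, because new damage on an unassessed item stays unseen. In the case of 5% missing at both times, the mean is 0.18 rather than the 0.19 of the current rule, which benefits there from two errors that partly cancel. The gain is that an unassessed item no longer produces false healing or false accrual, and the result does not depend on such cancellation.

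The cost is a few lines of SAP text and simple programming, with no new data collection.
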